## **9.4 Potential Benefits**

Based upon guidance provided in 45 CFR 46, subpart D regarding research in children, the proposed study presents greater than minimal risk without direct benefit to the individual subject (45 CFR part 46.406). However, this study has potential to yield generalizable knowledge about the subject's pharmacokinetics and dynamic response (45 CFR 46.406) to cortisol. An indirect benefit is this alternative pulse dosing strategy could spur the development of novel methods of HC drug delivery that could improve long term outcomes of patients with CAH.

## 10 Safety and Adverse Events

### 10.1 Definitions

#### **Adverse Event**

An **adverse event** (AE) is any symptom, sign, illness or experience that develops or worsens in severity during the course of the study. Intercurrent illnesses or injuries will be regarded as adverse events. Abnormal results of diagnostic procedures are considered to be adverse events if the abnormality:

- results in study withdrawal
- is associated with a serious adverse event
- is associated with clinical signs or symptoms
- leads to additional treatment or to further diagnostic tests
- is considered by the investigator to be of clinical significance

#### **Serious Adverse Event**

Adverse events are classified as serious or non-serious. A **serious adverse event** is any AE that is:

- fatal
- life-threatening
- requires or prolongs a hospital stay
- results in persistent or significant disability or incapacity
- a congenital anomaly or birth defect
- an important medical event

Important medical events are those that may not be immediately life threatening, but are clearly of major clinical significance. They may jeopardize the subject, and may require intervention to prevent one of the other serious outcomes noted above. For example, drug overdose or abuse, a seizure that did not result in in-patient hospitalization, or intensive treatment of bronchospasm in an emergency department would typically be considered serious.

All adverse events that do not meet any of the criteria for serious should be regarded as **non-serious adverse events**.

#### **Adverse Event Reporting Period**

The study period during which adverse events must be reported is normally defined as the period from the initiation of any study procedures to the end of the study treatment follow-up. For this study, the study treatment follow-up is defined as 30 days following the last administration of study treatment.

#### **Preexisting Condition**

A preexisting condition is one that is present at the start of the study. A preexisting condition will be recorded as an adverse event if the frequency, intensity, or the character of the condition worsens during the study period.

#### **General Physical Examination Findings**

## Interval Bolus Delivery of Cortisol in Children with CAH

At screening, any clinically significant abnormality will be recorded as a preexisting condition. At the end of the study, any new clinically significant findings/abnormalities that meet the definition of an adverse event will also be recorded and documented as an adverse event.

### **Post-study Adverse Event**

All unresolved adverse events will be followed by the investigator until the events are resolved, the subject is lost to follow-up, or the adverse event is otherwise explained. At the last scheduled visit, the investigator will instruct each subject to report any subsequent event(s) that the subject, or the subject's personal physician, believes might reasonably be related to participation in this study.

### **Hospitalization, Prolonged Hospitalization or Surgery**

Any adverse event that results in hospitalization or prolonged hospitalization will be documented and reported as a serious adverse event unless specifically instructed otherwise in this protocol. Any condition responsible for surgery should be documented as an adverse event if the condition meets the criteria for an adverse event.

Neither the condition, hospitalization, prolonged hospitalization, nor surgery are reported as an adverse event in the following circumstances:

- Hospitalization or prolonged hospitalization for diagnostic or elective surgical procedures for a preexisting condition. Surgery should **not** be reported as an outcome of an adverse event if the purpose of the surgery was elective or diagnostic and the outcome was uneventful.
- Hospitalization or prolonged hospitalization required to allow efficacy measurement for the study.
- Hospitalization or prolonged hospitalization for therapy of the target disease of the study, unless it is a worsening or increase in frequency of hospital admissions as judged by the clinical investigator.

## **10.2 Recording of Adverse Events**

At each contact with the subject, the investigator must seek information on adverse events by specific questioning and, as appropriate, by examination. Information on all adverse events will be recorded immediately in the source document, and also in the appropriate adverse event module of the case report form (CRF). All clearly related signs, symptoms, and abnormal diagnostic procedures results will be recorded in the source document, though should be grouped under one diagnosis.

All adverse events occurring during the study period must be recorded. The clinical course of each event will be followed until resolution, stabilization, or until it has been determined that the study treatment or participation is not the cause. Serious adverse events that are still ongoing at the end of the study period must be followed up to determine the final outcome. Any serious adverse event that occurs after the study period and is considered to be possibly related to the study treatment or study participation should be recorded and reported immediately.

## **10.3 Reporting of Serious Adverse Events**

### **10.3.1 IRB Notification by Investigator**

Reports of all serious adverse events (including follow-up information) must be submitted to the IRB within 5 working days if it falls under the UPIRTSO guidelines. Copies of each report and documentation of IRB notification and receipt will be kept in the Clinical Investigator's binder.

### **10.3.2 FDA Notification by Sponsor**

The study sponsor shall notify the FDA by telephone or by facsimile transmission of any unexpected fatal or life-threatening experience associated with the use of the drug as soon as possible but no later than 7 calendar days from the sponsor's original receipt of the information.

If a previous adverse event that was not initially deemed reportable is later found to fit the criteria for reporting, the study sponsor will submit the adverse event in a written report to the FDA as soon as possible, but no later than 15 calendar days from the time the determination is made.

Agency	Criteria for Reporting	Timeframe	Form to Use	Submission address/fax numbers
U of MN IRB	SAE : fatal, life-threatening or serious, unexpected, at least possibly related	5 working days	MedWatch 3500A Form	MMC 820
FDA	SAE : fatal, life-threatening, unexpected, at least possibly related	7 calendar days	MedWatch 3500a Form but alternative formats are acceptable (e.g. summary letter)	Fax: [name]
	SAE : serious, unexpected, at least possibly related	15 calendar days		

### **10.4 Stopping Rules**

Subjects will be removed from the study if the following occur:

- An infection at the site of SQ cannulation. On the first and second occasion of an infected site, the cannula will be changed and moved to a new SQ location, and the family will receive additional training in proper hygienic technique. If infection occurs on more than two occasions, poor hygienic technique might be a cause and the patient will be removed from the study.
- A systemic allergic reaction at the site of the SQ infusion cannula; if this happens we will discontinue using the pump and return a child to their oral HC therapy.
- If a patient experiences more than two episodes of adrenal crisis (defined as a constellation of signs and symptoms caused by low cortisol that include: lethargy, hypoglycemia, low blood pressure, vomiting/nausea, abdominal pain, weakness, dizziness and cardiovascular collapse) in the SQ treatment period, the patient will be removed from the study. Periods of increased stress or illness can result in adrenal crisis and can occur in any CAH patients at any time. The adrenal crisis would be attributed to the pump if there are no other triggers such as trauma, febrile illness, gastroenteritis. Patients will be instructed to take stress dose oral steroids during physical stress as per emergency protocol that all children with CAH receive as part of standard care, in addition to the cortisol provided by the SQ pump

## **10.5 Medical Monitoring**

The Principal Investigator will oversee the safety of the study at the University of Minnesota site. This safety monitoring will include careful assessment and appropriate reporting of adverse events as noted above. Medical monitoring will include a regular assessment of the number and type of adverse events.

This study will have a medical monitor, a University of Minnesota physician, not involved in the trial. The medical monitor will review adverse events, Serious Adverse Events, and any other event considered to be reportable to the University of Minnesota Institutional Review Board. The Principal Investigator will submit copies of these reports to the medical monitor.. The medical monitor will summarize its findings and/or recommendations in a letter to the Principal Investigator. The Principal Investigator will submit a copy of the monitor's report to the Institutional Review Board per their policy.

# **11 Statistical Considerations**

## **11.1 Primary Outcomes Measure**

**Primary objective 1:** Time periods of hyper- and hypocortisolemia and over- and under-suppression of 17OHP and D4A will be compared between the oral and SQHC PKPD admissions using a paired t-test (with times log-transformed if needed to satisfy the normality assumption). A sample of 8 children gives 80% power to detect a population-average difference in outcome (undesired time period) between oral HC and SQHC pump of 1.2 times the standard deviation describing variation between children in the outcome for oral HC minus the outcome for SQHC pump (Cohen's  $d=1.2$ ). This study design and analysis have not been performed to our knowledge in humans or animals, and data to estimate this standard deviation do not exist.

## **11.2 Secondary Outcomes Measures**

Statistical analysis for secondary measures of actigraph, quality of life, sleep survey and NIH toolbox: Descriptive statistics for each outcome variable will be provided and used to discern changes in the outcome variables. Repeated measures ANOVAs will be used to examine differences in each outcome variable from Oral HC to SQHC Pump, and then back to Oral HC.

Statistical analysis for VCORT: Correspondence between VCORT and salivary cortisol by LC-MS/MS (56 samples total) will be described using a scatter plot identifying the child who provided each measurement; the intra-class correlation (ICC) describing association of VCORT with LC-MS/MS; a test for bias of VCORT relative to LC-MS/MS using a paired t-test; and percentiles of absolute differences between the VCORT and LC-MS/MS measurements (e.g., "90% of differences were less than X").

The Likelihood Ratio Test will be used to determine the statistical significance of the changes in PKPD parameters. The difference between objective function values (OFV; a goodness of fit measure similar to a sum of squares) is approximately chi-square distributed and if the OFV decreases by more than 3.8 (chi-square,  $p=0.05$ ,  $df=1$ ) the model with the added parameter is significantly better. No formal power calculations are currently available for the NLME modeling approach. If a persistent difference within subjects exists among the TVCL estimates across the 3 PKPD treatment arms, it will be detected as a significant difference among THETA1, THETA2 and THETA3.

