### **3.2 Secondary/Exploratory Objectives**

1. Physical activity levels: Daily activity and sleep patterns will be assessed by wearing an Actigraph Link accelerometer (Pensacola, FL) for 7 full days (5 weekdays and 2 weekend days) during each study period.
2. Quality of Life and cognitive measures: Quality of life (QoL) measures including NIH toolbox will be measured four times during the study (baseline, and once during each study period). QoL will be measured through the validated PedsQL™ Generic Core Scale and the PedsQL™ Fatigue Scale. *NIH Toolbox Cognitive Tasks*: We will use NIH Toolbox Dimensional Change Card Sort Test (DCCS) from the computer-administered NIH Toolbox to measure children's attention and executive functioning and cognitive flexibility, along with the Flanker Inhibitory Control & Attention Test. A validated sleep and mood survey will also be administered.
3. This proposal will include a utility assessment of a real-time (20 minutes) noninvasive point-of-care salivary testing device [VerOFy® cortisol (VCORT)] in a home setting. While we are not using VCORT to make dosing decisions or diagnoses and formal monitoring will be accomplished using serum cortisol sampling within the protocol, we believe it is important to determine the utility of such a device.
4. An analysis to determine whether PKPD system parameters change with the switch in the route of HC administration from oral to SQHC pump, and after six weeks of SQHC treatment. A preferred pharmacometric analysis for this outcome is to use nonlinear mixed-effects (NLME) regression modeling to estimate PKPD parameters from all data at weeks 1, 7 and 14 simultaneously.

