### **5.2 Eligibility Criteria**

A total of 12 children (6 boys and 6 girls), aged 3-18 years, may be enrolled on this study, to ensure available analysis of 8 completed participants. This study entry is open to children regardless of gender or ethnic background.

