#### **6.2.2 Weeks 9-14 (SQHC Pump)**

### **6.2.2.1 Weeks 9-13**

Week 9 (outpatient visit) The patient will meet [name] and the study nurse coordinator at Nucleus (Prism) for initiating the 6-wk SQHC pump phase. The patient will have a physical exam and the nurse coordinator will review the patient's recorded daily blood pressure, subject diary, adverse events and any medications taken. It is our standard policy to make sure that families have parenteral hydrocortisone to use during emergencies. We will instruct the patients to call [name] before administering any parenteral dose during this phase. After the first four supervised home visits by the nurse coordinator, the family, as instructed will replace the HC infusion syringe and solution, and the site of SQ infusion every 72 hours. As with insulin, we recognize that there may be variability in drug absorption associated with different sites of SQ injection pump infusion therapy. Each subject will be evaluated for appropriate site for SQ infusion (i.e. gluteal area, abdominal area).. Parents will be instructed to visually inspect the parenteral HC solution for particulate matter and discoloration prior to administration into the pump.

After the outpatient visit, during week 9, the subject/family will be called on the days that the RN coordinator is not completing home visits. This call is the review pump use, adverse events and other questions or concerns.

Weeks 9-13: The nurse coordinator will visit subjects at home seven times for safety monitoring, which includes a nursing assessment, and measurement of cortisol, 17OHP, ACTH and D4A concentrations during the SQHC pump period. During the home visits, along with the blood draws, saliva will be collected and measured through VerOFy® cortisol (VCORT) with the remaining salivary sample sent to Quest Diagnostics for free cortisol measurements through LC-MS/MS assay. VCORT is IDE exempt per the requirements outlined in 21CFR812.2(c) and in 21CFR809.10(c). The nurse coordinator will complete their assessment and review the patient's recorded daily blood pressure, subject diary, adverse events and any medications taken. At Visit 13, an Actigraph Link accelerometer will be provided for monitoring daily activity and sleep patterns for one week.

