To note, the use of the VerOFy® may be restricted based upon the company's availability to provide the device to our site site. As noted under the secondary/exploratory objectives, the VerOFy® will not be used to "make dosing decisions or diagnoses and formal monitoring will be accomplished using serum cortisol sampling." We therefore will collect and record results only at time of availability for use of the device. The informed consent will notify participants/families that this sampling and measurement will be based upon when the device is available at the time of study visit..

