## **9.3 Methods to minimize risk**

Subjects will be monitored as per standard of care during treatment with oral cortisol. During the treatment with the SQHC pump, subjects will be monitored inpatient through physical exams for the first 36 hours. Following discharge, for the first four changes in SQ infusion site, a nurse coordinator will travel to the patient's home to evaluate proficiency in changing the injection site; to collect blood for cortisol, 17OHP, ACTH and D4A concentrations; and to inspect the injection site integrity. All patients will be seen at home twice during the first week and second week and once a week thereafter while on the pump. As an additional safety measure for monitoring pump failure that does not trigger an alarm, families will be given and instructed on how to use an automatic, upper arm blood pressure monitor with a cuff appropriate for the child's size. One week prior to the SQHC pump treatment, patients while on oral HC will measure and log child's blood pressure daily in the morning, after 5 minutes rest. When the child is on the pump, families will be instructed to measure and log the child's blood pressure daily. If the mean arterial pressure [MAP =  $[(2 \times \text{diastolic}) + \text{systolic}] / 3$ ] is less than 20 percent of the lowest MAP observed during oral treatment, the blood pressure will be measured 2 more times at 5-minute intervals. Instructions will be provided to the families to notify the PI if 2 of the 3 MAP measurements are below 20 percent of the lowest MAP obtained during oral HC treatment. Parents will be asked to inspect the injection site, tubing, and syringe volume. If no issues are identified and if the blood pressure remains outside the appropriate range after three measures, the parents will be instructed to bring the child to the clinic for clinical evaluation and assessment of pump function. Subjects and their parents will be instructed to contact the Principal Investigator immediately if they develop any signs of symptoms of adrenal insufficiency (e.g. fatigue, nausea, dizziness). The PI can be reached 24 hours a day by her pager number.

The parents of the subjects will be thoroughly trained on the use of the pump, the infusion sets which will be used, and the operational functions of the alarms.

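### The VCORT bias test in section 11.2 has no child-level term for 56 saliva pairs that appear to be 7 from each of 8 children, so positive within-child correlation would inflate its false-positive rate

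*Combined protocol and SAP*

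**What the plan says.** Section 11.2 plans four VCORT summaries: a scatter plot, an intra-class correlation between the two assays, "a test for bias of VCORT relative to LC-MS/MS using a paired t-test", and percentiles of the absolute assay differences. The only sample size is in the opening words: "LC-MS/MS (56 samples total) will be described using a scatter plot identifying the child who provided each measurement". The child enters as a plotting label and nowhere else. No averaging by child, random effect, cluster adjustment or df is named.

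The number of children comes from section 5.2, which enrols up to 12 "to ensure available analysis of 8 completed participants". The number of samples per child comes from section 6.2.2.1: "The nurse coordinator will visit subjects at home seven times for safety monitoring". At each of these visits both assays are run on the same saliva. Section 9.3 gives the visit pattern: "All patients will be seen at home twice during the first week and second week and once a week thereafter while on the pump".

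Section 6.2.2.1 also makes collection depend on device supply: "We therefore will collect and record results only at time of availability for use of the device". Section 3.2 limits the role of the device: "While we are not using VCORT to make dosing decisions or diagnoses".

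**The concern.** A paired t-test deals with the pairing of two assays on one sample. It does not deal with correlation among the several differences that one child contributes. If some children's saliva makes the device read consistently high or low, those differences move together and 56 pairs carry less information than 56 independent ones. The pooled standard error is then too small, and a device bias may be declared that the data do not support.

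The planned intra-class correlation does not fill the gap, because it describes association between the assays and not clustering by child. Elsewhere the plan does signal its unit. Section 11.1 bases the primary paired t-test on 8 children and on variation between them, and section 11.2 uses repeated-measures ANOVA for the actigraphy, quality-of-life, sleep and cognitive outcomes. The VCORT test has neither safeguard, although it is the only hypothesis test named for the device objective in section 3.2.

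**Working it through.** **Reproducing the plan's figure.** Section 9.3 gives 2 + 2 visits in the first two pump weeks, then one in each of weeks 11, 12 and 13, which makes 7. Then 8 children × 7 visits = 56, as stated. The alternatives 8 × 8 = 64 and 12 × 7 = 84 do not match.

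**Assumptions.** The documents give no significance level for this test, so a two-sided 5% level is assumed. They give no within-child correlation ρ of the VCORT minus LC-MS/MS differences, so a range is shown. Differences are taken as normal with equal correlation within a child and no true bias.

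**Formulas.** With m = 7 samples from each of k = 8 children (n = 56):

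- Design effect: DE = 1 + (m − 1)ρ = 1 + 6ρ. Effective sample size: 56/DE.
- The mean difference has variance σ²·DE/56.
- Between-child sum of squares: σ²·DE·χ² on 7 df. Within-child sum of squares: σ²·(1 − ρ)·χ² on 48 df.
- Pooled test: t = mean / √[(between + within)/(55 × 56)], referred to t on 55 df.
- Child-mean test: t = mean / √[between/(7 × 56)], referred to t on 7 df.

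Example at ρ = 0.3: DE = 1 + 6 × 0.3 = 2.8 and effective n = 56/2.8 = 20. The large-sample approximation 2[1 − Φ(1.96/√2.8)] gives 24.2%, against 24.7% from the simulation.

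**Results** (400,000 draws per row from the distributions above):

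| ρ | DE | Effective n | Pooled test rejects | Child-mean test rejects |
|---|---|---|---|---|
| 0 | 1.0 | 56.0 | 5.0% | 5.0% |
| 0.05 | 1.3 | 43.1 | 8.5% | 5.0% |
| 0.1 | 1.6 | 35.0 | 12.1% | 4.9% |
| 0.2 | 2.2 | 25.5 | 18.7% | 5.0% |
| 0.3 | 2.8 | 20.0 | 24.7% | 5.0% |
| 0.5 | 4.0 | 14.0 | 34.1% | 5.0% |
| 0.7 | 5.2 | 10.8 | 41.2% | 5.0% |

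Direct simulation of the 8 × 7 layout (100,000 replicates) agrees: 12.1%, 24.6% and 33.9% at ρ = 0.1, 0.3 and 0.5. At ρ = −0.05 the pooled test is conservative, at 1.9%.

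**Uneven counts.** Device supply may leave gaps. With assumed counts of 7, 7, 6, 5, 4, 3, 2 and 1 (35 pairs), the pooled test rejects 5.0%, 7.5%, 10.1%, 20.1%, 28.6% and 36.2% at ρ = 0, 0.05, 0.1, 0.3, 0.5 and 0.7. The child-mean test gives 4.3% to 5.0%.

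**Interval width, child-mean to pooled** (mean 95% CI width, in SDs of a single difference). For 8 × 7: 0.610/0.533 = 1.14 at ρ = 0, 0.772/0.530 = 1.46 at 0.1 and 1.020/0.523 = 1.95 at 0.3. For the uneven counts at ρ = 0: 0.930/0.682 = 1.36.

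**The case against.** **The defect is inferred.** Section 11.2 does not say that the test runs on 56 rows, and the plan's other paired t-test takes the child as its unit. This is fair as far as it goes. But 56 is the only count given for VCORT and no averaging is mentioned, so an analyst following the text would pool. If child means were intended, the same added sentence settles it.

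**The layout is inferred too.** No section states 7 samples from each of 8 children. Children who do not complete could also supply pairs, and the Schedule of Events seems to show an eighth home entry, which may come from how the table was read. The exact counts may therefore differ, but the direction of the problem does not.

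**The correlation may be small.** Both assays use the same saliva, so the child's true cortisol level largely cancels from the difference. What remains is assay error plus any child-specific interference or level-dependent error. At ρ = 0.02 the pooled test rejects only about 6.4%. This stands: nothing in the documents supports the upper rows of the table, and they should not set the weight of the point. Even so, ρ = 0.1 more than doubles the error rate.

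**The stakes are low.** The device assessment is exploratory, mostly descriptive, and tied to no decision rule. This also stands and limits the importance of the point.

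**Child means change the weighting.** With uneven counts, a child with one sample counts as much as a child with seven. With the counts above and ρ = 0, the standard deviation of the estimated bias rises from 0.169 to 0.207. This is a real cost and belongs in the choice of method.

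**Conclusion.** The concern holds. Read literally, the VCORT bias test treats repeated samples from the same children as independent, and its error rate exceeds the nominal level at every positive within-child correlation examined. The inflation is modest at small correlations (8.5% at 0.05, 12.1% at 0.1) and large only if the correlation is large. At zero correlation the pooled test is valid.

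The size rests on three assumptions: the inferred 8 × 7 layout, a two-sided 5% level, and a correlation that the documents do not give. With equal counts the bias estimate itself is unaffected; only its standard error and p-value are. The scatter plot and percentiles stand as descriptive summaries. The change is worth making before analysis because the unit is unstated and uneven counts are foreseeable.

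**What to change.** Add one sentence to section 11.2: bias is tested by a one-sample t-test on each child's mean VCORT minus LC-MS/MS difference, with df equal to the number of contributing children minus 1 (7 for 8 children), and is reported with its 95% confidence interval. Keep the scatter plot and percentiles as descriptive summaries.

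If uneven counts are expected and equal weighting of children is unwelcome, name a random-child-intercept model instead and state its df in advance. With REML and df of children minus 1 (4,000 simulations per setting, ρ from 0 to 0.7), it rejected 2.2% to 5.6% with equal counts and 1.5% to 5.6% with the uneven counts. It is therefore conservative when the correlation is near zero.

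No new data are needed. The price is a wider interval. With equal counts, the loss when the correlation is truly zero is the factor of 1.14; with the uneven counts it is 1.36. The larger factors of 1.46 and 1.95 at correlations of 0.1 and 0.3 arise where the pooled interval is itself too narrow, so they mainly correct overstated precision.
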